5.1.2.4 Dose Escalation Decisions for Monotherapy and Combination (Parts 1A and 1B)

The dose escalation phase of the study will evaluate the safety and tolerability of BMS-986207, given alone or in combination with nivolumab, based on DLTs, using a BLRM model (for BMS-986207 as monotherapy) and a BLRM-copula model (for BMS-986207 in combination with nivolumab).

Combination dose escalation (Part 1B) will not begin until 3 dose cohorts (i.e., 20 mg, 80 mg and 240 mg) have been determined to be safe in monotherapy dose escalation (Part 1A). During the dose escalation phase, a set of approximately 3 participants will be treated at each specified dose level. Cohort tolerability assessment and subsequent dose recommendation will occur when at least 2 evaluable participants within a cohort have completed a 4-week DLT period. Any toxicities that occur beyond the 4-week DLT period will be accounted for in making dose level decisions and/or dose level modifications.

If the potential DLT occurring in the third evaluable participant regarding the specific dose level does not influence the dose recommendation by BLRM or the BLRM-Copula model, the next dose level may proceed without waiting for the third participant to complete the corresponding DLT observation period, after discussion and agreement between the Sponsor and Investigators. Continuous re-assessment of dose recommendation, by BLRM in the escalation phase and BLRM-Copula in the combination phase, will be carried out for each dose level. Planned dose levels for dose escalation are provided in [Table 5.1.2.4-1](#). Planned dose levels may be modified, or intermediate dose levels added, based upon the BLRM analysis.

Table 5.1.2.4-1: Planned Doses During Part 1B (Combination Dose Escalation)

Dose Level/Cohort	BMS-986207	Nivolumab	Dose Schedule
1	80 mg	240 mg	q2w
2	240 mg	240 mg	q2w
3	480 mg	480 mg	q4w
4	1600 mg	480 mg	q4w

The RP2D dose of BMS-986207, alone and in combination with nivolumab, selected for cohort expansion will be based on evaluating the recommendation from BLRM and an overall assessment of all available safety, PK/█ and efficacy data.

Once the safety (during DLT evaluation) of a dose level has been established (Part 1A and/or Part 1B), additional participants (up to a total of 15) may be added to that dose level, to better characterize the PK, safety █ profiles █ assessments.

5.1.2.5 Dose Limiting Toxicities in Dose Escalation Phases (Parts 1A and 1B)

For the purpose of guiding dose escalation, DLTs will be defined based on the incidence, intensity, and duration of AEs for which no clear alternative cause is identified. The DLT period will be 28 days (4 weeks) in Part 1A and 28 days (4 weeks) in Part 1B. Any toxicities that occur beyond the 4-week DLT period will be accounted for in making dose level decisions.

For the purpose of participant management, any AE that meets DLT criteria, regardless of the cycle in which it occurs, will lead to discontinuation of study drug. Participants who withdraw from the study during the DLT evaluation period for reasons other than a DLT may be replaced with a new participant at the same dose level. The incidence of DLT(s) during the DLT evaluation period will be used in dose escalation decisions and to define the MTD. AEs occurring after the 4-week DLT evaluation period will be considered for the purposes of defining the RP2D upon agreement between the Sponsor, Medical Monitor, and Investigators, if the AEs are determined to have no clear alternative cause and are not related to disease progression.

Participants experiencing a DLT will not be retreated with study drug and will enter the safety follow-up period of the study. AEs will be graded according to the NCI CTCAE v4.03.

5.1.2.6 Safety Evaluation Phase of Part 1C

Up to 18 participants per dose level tested will be treated in the Triplet Cohort. BMS-986207 will be administered at 600 mg and/or 360 mg q3w and nivolumab will be administered at 360 mg q3w. Ipilimumab, at a dose of 1 mg/kg, will be given q6w. The DLT period in Part 1C will be 42 days (6 weeks).

A dose of 1200 mg BMS-986207 administered every 3 weeks has been tested per Amendment 03 but due to the DLTs observed no additional participants will be tested at this dose (see [Section 3.2.1.4](#)).

The DLT safety monitoring during the dose evaluation phase, including the potential decision to de-escalate to a lower dose, will be based on the BOPIN design framework with target toxicity (DLT) rate of 30% (24%, 36%), as presented in [Table 5.1.2.6-1](#).^{23,24} The BOPIN design takes a very simple form, rendering it easy to implement in practice. It is more straightforward and transparent than other model-based and model-assisted methods. The decisions on dose tolerability guided by the design are based on comparing the observed DLT rate at the current dose with a pair of fixed dose escalation and de-escalation boundaries. This allows generation of a decision table that guides DLT assessment depending on the number of participants treated and observed DLTs. The performance of the design based on the operating characteristics is shown in [Appendix 12](#).

As a dose escalation is not planned in Part 1C, a design recommendation to declare a dose as tolerable is based on meeting the same criteria needed to escalate. A minimum of 6 DLT evaluable participants will be required in Part 1C to declare a dose tolerable for initiation of Part 2C. In addition, to better estimate tolerability of the dose level in combination with nivolumab and ipilimumab, more participants will be treated even if a dose is declared tolerable with n=6, for up to a total of 18 treated. In contrast, a design recommendation “Stay” indicates that this dose level needs to be evaluated further for safety to declare this dose tolerable. In that case, additional cohorts of 3-4 or more participants (depending on the number of observed DLTs) will be treated up to a total of 18. If dose-de-escalation is recommended by the design based on the number of participants with DLTs observed during this dose evaluation phase ([Table 5.1.2.6-1](#)), then the next lower dose level will be used (360 mg BMS-986207 q3w) for the remaining participants as well as for those currently on treatment. In addition, other lower doses of BMS-986207 (200 mg q3w) than that seen as safe and tolerable may also be tested.

Initially, the first 3 to 4 participants treated in the Triplet Cohort will be evaluated for DLTs. If 0 or 1 DLT is observed during the 6-week DLT period, an additional 3-4 participants will be treated at the same BMS-986207 dose level. If ≤ 1 DLTs are observed out of the first 6 DLT-evaluable participants, the dose will be considered safe. If 2 DLTs are observed out of 6 DLT-evaluable participants, an additional 3-4 participants will be enrolled. If ≤ 3 DLTs are observed out of 9 DLT-evaluable participants, an additional 3 participants will be enrolled. If 2 DLTs are observed out of 12 DLT evaluable participants, the dose level will be considered safe.

If 3 or 4 DLTs are observed out of 12 DLT evaluable participants as shown in [Table 5.1.2.6-1](#), the design recommends to stay at the same dose level, indicating that more participants may need to be evaluated to determine whether the dose level is safe. After considering additional information such as provided in [Table 5.1.2.6-2](#) and the totality of available data including safety, PK/pharmacodynamics from all treated participants, a lower dose may be considered for evaluation, (eg, if 4 /12 DLTs) or the dose may be considered safe (eg, with 3/12 DLTs) based on discussion between the Investigator and Sponsor/Medical Monitor, and based on posterior probability of the DLT rate exceeding the target. Once a dose is declared safe based on at least 6 participants, an additional 6-12 participants may be treated up to a total of 18 to continue to confirm the safety of the selected dose. At the same time, enrollment in Part 2C may begin. In addition, another cohort up to 18 participants may be treated at the next lower dose of BMS-986207 to optimize dose selection. Participants who do not complete the DLT observation period for

reasons other than DLTs may be replaced. De-escalation may be considered if the safety and tolerability profile for the selected BMS-986207 dose is evaluated as not acceptable, after discussion between the Investigator(s) and the Sponsor/Medical Monitor.

Table 5.1.2.6-1: Triplet Safety Evaluation Guidance for DLT-Related Decisions by BOIN Design Framework

Actions based on number of DLT's	The number of DLT-evaluable participants treated at the current dose									
	3	4	5	6	7	8	9	10	11	12
Declare dose tolerable if # of DLT \leq^a	0/NA	0/NA	1/NA	1	1	1	2	2	2	2
Stay if # of DLT =	1	1	NA	2	2	2	3	3	3	3,4
De-escalate if # of DLT \geq	2	2	2	3	3	3	4	4	4	5
Eliminate if # of DLT \geq	3	3	4	4	5	5	5	6	6	7

Abbreviations: BOIN, Bayesian optimal interval; DLT, dose-limiting toxicity

^a The decision meets the same requirements as needed to “escalate” in standard design. NA indicates that decisions to declare a dose tolerable will not be made with fewer than 6 participants

In addition to the above guidance, the following posterior probability may be considered to guide the DLT tolerability decision. Assuming a 33% acceptable DLT rate in triplet, which corresponds to a Beta (1, 2) distribution, Table 5.1.2.6-2 shows the chance of confirming a BMS-986207 dose level as safe based on the observed DLTs and expressed as a posterior of DLT probability given the number of DLTs observed in the first 6, 9, or 12 participants during the triplet evaluation phase.

Table 5.1.2.6-2: Posterior Probability of DLT in Triplet Cohort Assuming Observed Data

Number of Participants at a Dose level	Number of Participants with an Observed DLT	Probability of DLT Rate >30%	Probability of DLT Rate >33%	Probability of DLT Rate >40.0%
6	1	0.26	0.2	0.11
6	2	0.55	0.47	0.32
9	2	0.31	0.24	0.12
9	3	0.57	0.48	0.30
12	2	0.16	0.11	0.04
12	3	0.36	0.27	0.12
12	4	0.58	0.48	0.28

Abbreviations: DLT, dose-limiting toxicity.

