5.2 Number of Participants

The approximate number of evaluable participants will be approximately 241. Approximately 100 of these participants will be treated with monotherapy and combination therapy dose escalation (35 participants each for Part 1A and Part 1B and additional 30 participants for the substudy of

Part 1B), and approximately 36 participants treated (6 initial participants for safety evaluation followed by evaluation of approximately 12 additional participants per dose level) with BMS-986207, nivolumab, and ipilimumab in the Triplet Cohort (Part 1C). The remaining participants (up to 105) will be treated as part of dose expansion, with up to 24 participants in Part 2A and 41 participants in Part 2B, and 40 participants with NSCLC and [REDACTED]

[REDACTED] (pre-existing or prior PD-L1 IHC results from testing of tumor tissue) considered to be response-evaluable, in Part 2C. In the event more than 25% of the participants in Part 2C are found to have a PD-L1 tumor cell score of < 1%, based on central lab testing, additional participants may be enrolled in order to have at least 30 participants with a PD-L1 tumor cell score $\geq 1\%$.

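### Table 6 of Appendix 12, cited as the performance of Part 1C, simulates 12 participants in total with a selection rule the study does not use, and so overstates how often the higher dose would be declared tolerable

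*Combined protocol and SAP*

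**What the plan says.** Section 5.1.2.6 sets the size of Part 1C per dose: "Up to 18 participants per dose level tested will be treated in the Triplet Cohort". A dose can be declared tolerable from 6 DLT-evaluable participants, after which "more participants will be treated even if a dose is declared tolerable with n=6, for up to a total of 18 treated". Section 5.2 plans "approximately 36 participants treated (6 initial participants for safety evaluation followed by evaluation of approximately 12 additional participants per dose level", and Section 10.1.2 repeats the limit of about 18 treated per dose and says that BOIN guides the decisions.

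Table 5.1.2.6-1 gives DLT counts for declaring tolerable, staying, de-escalating and eliminating. It is indexed by "The number of DLT-evaluable participants treated at the current dose" and runs from 3 to 12. If the design recommends de-escalation, "then the next lower dose level will be used (360 mg BMS-986207 q3w) for the remaining participants". A later sentence on the chosen dose is softer: "De-escalation may be considered if the safety and tolerability profile for the selected BMS-986207 dose is evaluated as not acceptable". Once a dose is declared safe, more participants may be added; "At the same time, enrollment in Part 2C may begin".

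On performance, the section says: "The performance of the design based on the operating characteristics is shown in" Appendix 12. Section 5 of that appendix caps the sample at 12, in cohorts of 3, with boundaries 0.236 and 0.359. It describes choosing the MTD by isotonic regression at the end of the trial, and says that this is for general information and not applied here. Table 6 then prints selection percentages and average sizes of 11.8 to 12.0. The accompanying text concludes that a truly tolerable dose is very likely to be picked.

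**The concern.** Table 6 is what the protocol offers when a reader asks how often the Part 1C design reaches the right answer. Scenario 2, where the higher dose is exactly at the 30% target, shows that dose selected in 77.8% of trials. An investigator or ethics committee would take this as the chance that Part 1C clears such a dose. Scenarios 1 and 3 would likewise be read as the chance that a dose with a true DLT rate of 48% or 35% goes forward.

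Those readings fail if the simulated trial differs from the planned one. It differs in two visible ways: the sample size, and the rule that turns DLT counts into a decision. Isotonic selection must choose between the doses tried unless the trial stops early. Part 1C clears a dose only if its count falls at or below the lower boundary.

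**Working it through.** **1. Inputs.** Target 0.30; cohorts of 3; boundaries 0.236 and 0.359; Table 6 rates (Appendix 12, Section 5). Cap of 18 treated per dose and clearance from n=6 (Section 5.1.2.6). Assumed: looks exactly every 3, all participants evaluable, no return to the higher dose, the table (not the prose) followed at n=9, and a 0.95 elimination cutoff in the simulation.

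**2. Boundaries.** With the standard BOIN settings of 0.6 and 1.4 times the target (0.18 and 0.42):
- lower = ln(0.82/0.70) / ln[(0.30 × 0.82)/(0.18 × 0.70)] = 0.2365
- upper = ln(0.70/0.58) / ln[(0.42 × 0.70)/(0.30 × 0.58)] = 0.3585

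These agree with the appendix, and the tolerable, de-escalate and eliminate rows of Table 5.1.2.6-1 reproduce for n=3 to 12.

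**3. Reproducing Table 6.** Simulation with 12 participants in total, a start at the higher dose and isotonic selection (20,000 trials per scenario; lower dose / higher dose / early stop):

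| Scenario (true rates) | Printed | Simulated | Mean N printed / simulated |
|---|---|---|---|
| 1 (0.30, 0.48) | 60.8 / 31.9 / 7.3% | 60.5 / 31.9 / 7.5% | 11.8 / 11.83 |
| 2 (0.16, 0.30) | 22.1 / 77.8 / 0.1% | 21.9 / 77.6 / 0.5% | 12.0 / 11.99 |
| 3 (0.20, 0.35) | 33.7 / 65.2 / 1.1% | 33.4 / 65.3 / 1.3% | 12.0 / 11.97 |

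A start at the lower dose does not fit (scenario 1: 62.2 / 25.2%). Nor does 12 per dose (scenario 1: 63.0 / 26.3 / 10.8%, mean N 16.6). So Table 6 is 12 in total over both doses, with isotonic selection.

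**4. The Part 1C rule, exactly.** At each look, de-escalate if DLTs ≥ 0.359n; from n=6 declare tolerable if DLTs ≤ 0.236n; otherwise stay. Each cohort adds k DLTs with probability C(3,k) p^k (1−p)^(3−k). For p = 0.30 these are 0.343, 0.441, 0.189 and 0.027.

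Clearance at p = 0.30:
- n=6, ≤1 DLT: 0.7^6 + 6 × 0.3 × 0.7^5 = 0.1176 + 0.3025 = 0.4202
- n=9, ≤2: the state 2/6 (not stopped at n=3) has probability 0.343 × 0.189 + 0.441² = 0.2593; then no DLT: × 0.343 = 0.0889
- n=12, ≤2: impossible from 3/9
- n=15, ≤3: 0.2593 × 0.441 × 0.343 × 0.343 = 0.0135
- n=18, ≤4: the state 4/15 has probability 0.0173 + 0.0173 = 0.0346; × 0.343 = 0.0119

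The sum is 0.534. If the de-escalate row still binds, cleared doses later cross it with probability 0.008, 0.020, 0.021 and 0.018 at n=9, 12, 15 and 18 (for example, 1/6 then 3/3: 0.3025 × 0.027 = 0.008). The sum is 0.067, which leaves 0.467.

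The same recursion at the other rates gives, for the higher dose declared tolerable and kept:

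| True rate | Table 6 | Row lapses at clearance | Row binds to 18 | Gap to Table 6 (points) |
|---|---|---|---|---|
| 30% | 77.8% | 53.4% | 46.7% | 24.4-31.1 |
| 35% | 65.2% | 40.8% | 31.9% | 24.4-33.3 |
| 48% | 31.9% | 16.0% | 7.2% | 15.9-24.7 |

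**5. Selection rule or cap?** The same rule with a cap of 12 per dose gives, at 30%, 35% and 48%:
- row lapses: 50.9, 39.1 and 15.8%; the cap of 18 adds 2.5, 1.7 and 0.2 points
- row binds: 48.1, 35.5 and 11.7%; the cap of 18 removes 1.4, 3.6 and 4.5 points

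Either way, most of the distance from Table 6 is already there at 12 per dose.

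**6. Discretion at stay.** The plan lets the team judge a dose safe at, for example, 3/12. Suppose every dose still at stay at n=12 were counted as tolerable, with the row lapsing. The figures become 50.9 + 9.0 = 59.9%, 39.1 + 8.4 = 47.5% and 15.8 + 4.2 = 20.0%, still well below Table 6.

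**The case against.** The best defence is that the appendix hides nothing. It prints the limit of 12 and says that the isotonic step is not applied, so a careful reader can see that Table 6 is generic. On safety the error is also in the comfortable direction: Part 1C's own rule carries a dose with a 48% DLT rate forward about half as often as Table 6 suggests, or less. Table 6 is not the sole evidence either. Table 5.1.2.6-2 gives posterior probabilities of excess toxicity at 6, 9 and 12 participants, and Section 10.1.2 cites it for the risk of a dose selected as tolerable. Part 1C tests no formal hypothesis.

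All of that stands, and it limits the point to a wrong performance statement. It does not rescue the statement. Section 5.1.2.6 cites the appendix as this design's performance, and the favourable conclusion under Table 6 rests on the rule the study sets aside. Table 5.1.2.6-2 informs a decision once data are in; it does not say how often the design clears a dose.

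A reader might also infer that DLTs arising after clearance trigger nothing, or that the rule has no content beyond 12 participants. The documents do not support this. The mandatory de-escalation sentence in Section 5.1.2.6 follows the text on treating up to 18 and makes no exception for a cleared dose. Section 10.1.2 applies BOIN across the 18. The fixed boundaries give the counts for 13 to 18. Sections 3.3 and 5.1.5 provide ongoing safety review. What is missing is one explicit sentence, which would settle how the firm wording and the softer wording on the selected dose fit together.

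**Conclusion.** The concern holds for Table 6. The table describes 12 participants in total with isotonic selection, not the Part 1C rule, and its percentages for the higher dose are 16 to 33 points too high. A dose at the 30% target would be declared tolerable and kept in about half of trials, not 77.8%. The text's claim of a high chance of picking the tolerable dose is therefore not supported for such a dose. The table errs in both directions of interest: it is too optimistic about clearing a dose at target and too pessimistic about a too-toxic one getting through. It should not be read as showing that Part 1C is less safe than stated, nor that the move from 12 to 18 is the main cause.

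The figures assume looks every 3 and all participants evaluable. The 18 counts treated participants; at the 4-of-6 evaluable ratio seen at 1200 mg, 18 treated would give 12 evaluable, and the cap-of-12 figures above would apply. The conclusion is the same. The silence on de-escalation after clearance and the table's end at 12 are points of clarity, not errors.

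**What to change.** Replace Table 6 with operating characteristics for the rule Part 1C uses: declare tolerable at ≤0.236 from n=6, de-escalate at ≥0.359, up to 18 per dose. Report how often each dose is declared tolerable, de-escalated or left at stay, and the expected sample size. Revise the concluding sentence to match. This costs one rerun and a short text change; no participant or assessment is added. The downside is that the stated chance of clearing a dose at target becomes less favourable.

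Optional clarification in Section 5.1.2.6: say that the de-escalate row continues to apply after a dose is declared tolerable, and extend Table 5.1.2.6-1 with the counts the same boundaries imply.

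| Evaluable | Tolerable | Stay | De-escalate |
|---|---|---|---|
| 13 | ≤3 | 4 | ≥5 |
| 14-16 | ≤3 | 4-5 | ≥6 |
| 17-18 | ≤4 | 5-6 | ≥7 |

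If the row is made to bind, some acceptable doses will be de-escalated after clearance: 6.7/53.4 = 12.5% of cleared doses at a true 30%, and 2.0/79.1 = 2.5% at a true 20%.

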5.1.2.7 Cohort Expansion (Parts 2A, 2B, and 2C)

The purpose of cohort expansion is to gather additional safety, tolerability, preliminary efficacy, PK, [REDACTED] information regarding BMS-986207 alone and in combination with nivolumab. Continuous evaluation of toxicity events in the cohort expansions will be performed throughout enrollment in the expansion cohorts. If, at any time, the aggregate rate of treatment-related toxicities meeting DLT criteria exceeds 33% across all participants treated in cohort expansions 2A or 2B, the findings will be discussed and further enrollment will be interrupted. Depending on the nature and grade of the toxicity, and after assessing the risk/benefit ratio, a new dose for all cohorts may be initiated at a previously tested lower dose level or at a dose level intermediate to previously tested, lower dose levels.

In Part 2A, only CRC will be evaluated in cohort expansion with BMS-986207 as monotherapy. In Part 2B, the 3 disease-restricted populations, ovarian cancer, colorectal cancer (CRC) and HCC will be investigated in cohort expansions with BMS-986207 in combination with nivolumab. A Fleming 2-stage design framework will be used as a guide in cohort expansion.

During the cohort expansion phase, participants with CRC who have disease progression on BMS-986207 monotherapy will be able to cross over to combination treatment (BMS-986207 + nivolumab), once the CRC expansion arms (ie, monotherapy and combination therapy) are both enrolling. This cross-over option, for CRC participants only, is not applicable during the escalation phases.

The purpose of Part 2C is to gather preliminary efficacy information regarding BMS-986207 in combination with nivolumab and ipilimumab. Participants with advanced, treatment-naïve NSCLC whose tumors express PD-L1 will be treated with BMS-986207 in combination with nivolumab and ipilimumab. BMS-986207 will be administered at 600 mg q3w (or tolerable dose as determined in Part 1C) and nivolumab will be administered at 360 mg q3w. Ipilimumab, at a dose of 1 mg/kg, will be given q6w.

Part 2C may begin once there is sufficient safety data from a minimum of 6 participants in Part 1C.

Part 2C will enroll a minimum of 20 participants per dose level of BMS-986207. One or two doses are planned to be evaluated and selected from the range of doses assessed as tolerable and not exceeding the maximum tolerated dose in Part 1C. If two doses will be tested at the Sponsor's discretion, participants will be randomized in a 1:2 ratio schema between the highest dose selected in Part 1C and the next lower dose, after at least 10 participants will have been tested at the dose found safe in Part 1C.

Continuous evaluation of toxicity events will also be performed in this part of the study. If, at any time, the aggregate rate of treatment-related toxicities meeting DLT criteria exceeds 33% in Parts 2A or 2B, the findings will be discussed and further enrollment may be interrupted. In addition, a more guided continuous safety monitoring will be implemented in Part 2C, 1L NSCLC expansion, using a Bayesian framework and specific criteria based on a posterior probability of a DLT rate exceeding 33% implemented starting with n=6 ([Table 10.3.8-1](#)). Depending on the nature and

grade of the toxicity, and after assessing the risk/benefit ratio, a new BMS-986207 dose for all participants, including those currently on treatment, may be initiated at a lower dose level.

Participants with an outcome of unconfirmed progressive disease, stable disease (SD), partial response (PR), or complete response (CR), at the end of a given cycle, will continue to the next treatment cycle. Participants will be allowed to continue study treatment until the first occurrence of any of the following:

- Completion of the maximum number of cycles
- Confirmed PD (see [Section 5.1.4](#))
- Clinical deterioration suggesting that no further benefit from treatment is likely
- Intolerability to therapy
- Participant meets criteria for discontinuation of study treatment as shown in [Section 8.1](#)

5.1.2.8 *Treatment with Additional Cycles Beyond 24 Weeks (Parts 1A, 1B, 2A, and 2B)*

All participants will be treated for up to 24 weeks (3 cycles) with monotherapy (Parts 1A and 2A) or combination therapy (Parts 1B and 2B), unless treatment discontinuation criteria are met earlier ([Section 8.1](#)). Participants with ongoing disease control (CR, PR or SD) or unconfirmed progressive disease, after completing approximately the initial 24 weeks of treatment, may be eligible for an **additional 3 cycles of study therapy** in both the monotherapy (Parts 1A and 2A) and combination therapy (Parts 1B and 2B). These participants will be selected on a case by case basis, after careful evaluation and discussion with the BMS Medical Monitor, to determine whether the risk/benefit ratio supports administration of further study therapy. Upon completion of 3 cycles of study therapy (or up to a maximum of 6 cycles if applicable), all participants will enter the safety follow-up period.

Individual participants with confirmed CR will be given the option to discontinue study treatment, on a case by case basis, after specific consultation and agreement between the Investigator and BMS Medical Monitor in settings where benefit/risk justify discontinuation of study therapy.

5.1.3 *Follow-up*

5.1.3.1 *Safety Follow-up Period*

For participants in Parts 1A, 1B, 2A and 2B, upon completion of 3 cycles of study therapy (or up to a maximum of 6 cycles if applicable), and once the decision is made to discontinue the participant from treatment, ie, at end of treatment (EOT), all participants will enter a safety follow-up period.

In Parts 1C and 2C, participants can receive study treatments up to a maximum of 2 years in the absence of disease progression or unacceptable toxicity. Once a decision is made to discontinue treatment, the participant will enter a safety follow-up period.

For participants who complete all scheduled cycles of therapy, the EOT visit will be the same visit as the last scheduled and completed on-treatment visit, and will be the start of the safety follow-

up period. For participants who do not complete all scheduled cycles of therapy, the EOT visit will be the most recent on treatment visit (with all available safety and response data), and will not need to be repeated. Accordingly, for these participants, this visit will be considered the start of the safety follow-up period.

After the EOT visit, all participants will be evaluated for any new AEs for at least 100 days after the last dose of therapy. Follow-up visits should occur at Day 30, 60 and 100 (\pm 7 days) after the last dose, or the date of discontinuation (\pm 7 days). All participants will be required to complete the 3 clinical safety follow-up visits, regardless of whether new anti-cancer therapy is started, except those participants who withdraw consent for study participation.

